5.1.4.5 Pump removal

In the case of progressive disease or any other reason where use of pump/catheter in HAI group becomes obsolete and is not acceptable to the patient, the pump may be removed (at OUH, dept of GI surgery, HPB-section) through a local incision. The catheter will be ligated and left in situ. In the case of liver resection the catheter may be removed (with the pump) or left in situ, at the surgeon's discretion. During longer drug-free periods, a glycerol solution will be added in the pump chamber to prevent thrombosis of the catheter until the next treatment cycle. Post-resectional use of HAI will be off protocol.

5.1.4.6 Dosage of FUDR, Dexamethasone (Dex), proton pump inhibitors and pump administration.

All patients start HAIP chemotherapy 4 to 8 weeks after surgery, after confirmation of bilobar hepatic perfusion and lack of extrahepatic perfusion.

The pump reservoir is filled percutaneously with 0.12 mg/kg floxuridine together with 35,000U of heparin, 25 mg of dexamethasone and enough normal saline for a total volume of 35cc. Both are to be delivered as a 14-day continuous infusion through the pump. For patients who are more than 25% above ideal body weight, the actual dose of floxuridine is calculated by using a weight that averages the patient's actual weight and their ideal weight.

Patients will commence treatment at a minimum 2 weeks after pump placement. Therapy will be administered in a 4-week cycle. HAI therapy starts on day 1 of each cycle, and the pump will be emptied and filled with heparin (35,000 units) and normal saline on day 15. Systemic chemotherapy will be administered on day 2 and day 16 of each cycle.

Until completion of HAI chemotherapy, patients will receive prophylactic proton pump inhibitor 20mg once daily.

To assess early side effects and toxic reactions, patients will be hospitalized at the Gastrointestinal ward at Rikshospitalet for 24 hours following start of first FUDR administration. At later occasions, the treatment will be offered as an outpatient procedure.

5.1.4.7 Drug Information floxuridine.

The drug that is used for HAIP is fluorodeoxyuridine or floxuridine (FUDR, Fresenius Kabi, LLC, USA). Floxuridine has been administered using HAI pumps since the early 80s for patients with CLM in the adjuvant, neo-adjuvant, and induction chemotherapy setting. Floxuridine has a half-life of 10 minutes and the liver extracts 95% of floxuridine during the first pass. Toxic effects have been well characterized and are described in detail below. The most important serious adverse drug reaction is biliary toxicity.

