1.6 Hepatic artery infusion (HAI) chemotherapy for CRLM

The biological rationale for intra-arterial chemotherapy is that the hepatic artery rather than the portal vein is responsible for most of the blood supply to liver tumors. Hepatic Artery Infusion (HAI) of a cytotoxic drug floxuridine (FUDR) that has a very high first-pass extraction (ca 95 %) in the liver has shown promising results in selected series for several decades ¹⁴⁻¹⁶. It was developed at Memorial Sloan Kettering Cancer Center (MSKCC, New York, USA) but is currently unavailable in the European Union, because floxuridine is not registered. HAI has however not gained foothold as a standard treatment option for CRLM, and most publications stem from a very few centres. The reasons for this lack of dissemination are unknown but could well be related to the complexity of the treatment algorithm and the lack of modern randomized trials. In Europe several centers in The Netherlands have recently started the HAI treatment procedure as adjuvant treatment in CRC patients who have received liver resection. (Buisman FE et al. *Ann. Surg. Oncol.* 2019 26: 4599-4607. Of the 20 patients included in the study in The Netherlands two patients had Clavien-Dindo complication grade III with reoperation due to replacement of a pump with slow flow-rate and a flipped pump. The treatment administered both at MSKCC and the two centers in The Netherlands consist of 0.12 mg FUDR/kg/day + 35.000 IE heparin + 25 mg dexamethasone in a total volume of 35ml NaCL administered as a continue infusion for 14 days with dose reduction if liver function is affected (Table 2). At day 15 the pump is emptied and refilled with a low dose heparin solution for continuous infusion to avoid coagulation of the catheter. A new cycle is started at day 29. The HAI treatment has been combined with both oxaliplatin and irinotecan regimens combined with 5-FU as systemic chemotherapy ^{14,16,17}. HAI has also been

combined with systemic gemcitabine-oxaliplatin regimen in patients with non-resectable intrahepatic cholangiocarcinoma¹⁸

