1.7 Rationale for the Study and Purpose

The target population for this study will be patients who based on traditional preoperative criteria have a very dismal prognosis. They will – according to the inclusion criteria – have a large tumour burden and have shown progression on 1st line systemic chemotherapy treatment. Based on previous trials, only 30 % of this patient group will be alive after two years. These patients have today only one treatment modality available: 2nd line systemic chemotherapy. Response can, however, only be expected in a small minority of these patients. As of today, they are not acceptable for inclusion into any of the liver transplant protocols, and hepatic artery infusion (HAI) chemotherapy treatment is not offered in Norway (or any other European country, save the Netherlands, as far as we know).

With such a dismal outcome for these patients, an alternative modality that has the potential to improve survival is highly warranted. While transplantation has such a potential, the access to donor organs will always limit the real-life use of such a treatment and the inclusion of a transplant group in this trial is primarily for proof-of-principle reasons: to benchmark what we have reason to believe is the optimal treatment.

The use of HAI chemotherapy with FUDR has some inherent risks. A laparotomy is necessary to apply the catheter and intra hepatic infusion of FUDR has been reported to cause biliary inflammation and necrosis in a small fraction of the patients. The risk for the latter is however significantly reduced by concomittant steroid infusion. The experiences published from the MSKCC (see further) does however suggest that the drug has few systemic side effects as the first-pass effect in the liver is close to complete, i.e. there is minimal release of active drug into the systemic circulation.

The IMP for use in this protocol does not have a marketing authorization in Europa. The institution that has pioneered the HAI treatment in CRC is Memorial Sloan Kettering Hospital (MSKCC) in New York and the dose is identical to the dose that used in several studies from MSKCC^{14,16} and The Netherlands¹⁷.

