5.1.3 Hepatic Artery infusion (HAI)

Hepatic artery infusion will be administered via a pump (Tricumed IP2000V (tricumed Medizintechnik GmbH, [name]) titan infusion pump with a 35 ml reservoir (product no. 200 V 025 035 0WA) connected to a Brown silicone intraarterial catheter. The catheter is inserted into the gastroduodenal artery during a formal laparotomy. The treatment will be administered as established as standard operating procedure at Memorial Sloan Kettering Cancer Centre as previously described¹⁴⁻¹⁶. Patients in the HAI group will also receive systemic chemotherapy.

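### The floxuridine dosing instruction in 5.1.4.6 has lost its per-day unit and, read literally, gives at most 1/14 of the intended dose

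*Protocol*

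**What the plan says.** Protocol section 5.1.4.6 is the dosage section for the investigational drug. It states: "The pump reservoir is filled percutaneously with 0.12 mg/kg floxuridine together with 35,000U of heparin", adds 25 mg of dexamethasone, and makes the volume up to 35 cc with saline. It continues: "Both are to be delivered as a 14-day continuous infusion through the pump". At the end of the infusion "the pump will be emptied and filled with heparin (35,000 units) and normal saline on day 15".

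Section 1.6 describes the regimen used at the originating US centre and in the Netherlands as "0.12 mg FUDR/kg/day + 35.000 IE heparin + 25 mg dexamethasone in a total volume of 35ml NaCL", infused continuously for 14 days. It refers dose reductions to Table 2, which is this protocol's own table in 5.1.4.8.

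Two other places link the trial dose to that regimen without giving a number. Section 1.7 says that "the dose is identical to the dose that used in several studies" from those centres. Section 5.1.3 says: "The treatment will be administered as established as standard operating procedure at Memorial Sloan Kettering Cancer Centre". Section 5.1.3 also describes the device, a "titan infusion pump with a 35 ml reservoir".

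**The concern.** The two descriptions agree on heparin, dexamethasone, volume and duration. They differ only in the floxuridine unit: an amount per kg in 5.1.4.6, an amount per kg per day in 1.6. Both cannot describe the same 14-day infusion.

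The wording of 5.1.4.6 makes the wrong reading the natural one. It says what goes into the reservoir, and the heparin and dexamethasone in the same sentence are totals per fill. Nothing tells the reader to treat the floxuridine figure as a daily rate.

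This is the operative instruction for a cytotoxic drug that, by section 1.7, has no European marketing authorisation and belongs to a treatment not offered in Norway, so local habit is a weak safeguard. The dose adjustments in 5.1.4.8 are percentages, so an error in the starting dose would carry into every later one. If the literal fill were given, the HAI arm would receive a small fraction of the cited dose, and its comparison with control would say little about the regimen that motivates the trial.

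**Working it through.** **Inputs**

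| Item | Section 5.1.4.6 | Section 1.6 |
|---|---|---|
| Floxuridine | 0.12 mg/kg in the fill | 0.12 mg/kg per day |
| Heparin | 35,000 U | 35,000 IE |
| Dexamethasone | 25 mg | 25 mg |
| Volume | 35 cc | 35 ml |
| Infusion | 14 days, continuous | 14 days, continuous |

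Assumptions, not in the protocol: body weight 70 kg (range 50 to 100 kg) and pump flow, which is not stated.

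**Step 1: dose over one infusion**

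Dose over 14 days = daily dose x days.

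- Section 1.6: 0.12 x 14 = 1.68 mg/kg.
- Section 5.1.4.6 read literally, fully delivered: 0.12 mg/kg, or 0.12 / 14 = 0.0086 mg/kg per day.
- Ratio: 0.12 / 1.68 = 0.0714, that is 1/14 or 7.1%, at any weight.

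**Step 2: in milligrams**

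- At 70 kg: 1.68 x 70 = 117.6 mg intended, against 0.12 x 70 = 8.4 mg literal.
- From 50 to 100 kg: 84 to 168 mg intended, against 6 to 12 mg literal.

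**Step 3: does pump flow change this?**

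A 35 ml reservoir that runs continuously for 14 days allows at most 35 / 14 = 2.5 ml/day; at 3.0 ml/day it would be empty after 11.7 days. A slower flow is possible, because the pump is emptied on day 15 and may still hold fluid. Two formulas apply:

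- Delivered from the literal fill in 14 days = 0.12 x (14 x flow) / 35.
- Fill needed for 0.12 mg/kg per day = 0.12 x 35 / flow.

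| Assumed flow (ml/day) | Literal fill delivers in 14 days (mg/kg) | Share of 1.68 mg/kg | Fill needed (mg/kg) | Fill needed at 70 kg (mg) |
|---|---|---|---|---|
| 2.5 | 0.120 | 7.1% | 1.68 | 117.6 |
| 2.0 | 0.096 | 5.7% | 2.10 | 147.0 |
| 1.5 | 0.072 | 4.3% | 2.80 | 196.0 |

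So 1/14 is the smallest shortfall under the literal reading. A fixed fill of 1.68 mg/kg would also fall short at slower flow: 1.68 x flow / 35 gives 0.120, 0.096 and 0.072 mg/kg per day at these three flows, or 100%, 80% and 60% of target.

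**The case against.** The strongest reply is that the protocol resolves the conflict itself. Section 1.6 gives the per-day figure, 1.7 equates the trial dose with it, and 5.1.3, inside the treatment section, adopts the originating centre's procedure. Nothing supports 0.12 mg/kg per 14 days as a deliberate choice. Section 1.6 also lists a daily rate beside fixed totals, so 5.1.4.6 looks like the same shorthand with its time unit lost. Refills take place only at the trial hospital, the drug is prepared by pharmacy, and the harm depends on a misreading that three sections contradict.

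Most of this stands. It is a dropped unit rather than two competing regimens; the intended dose can be recovered; misdosing is not shown. That limits the weight of the point but does not make the sentence right. An operative dosing instruction should not need correcting from the Introduction.

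A second reply is that the flow scenarios and a fill formula go beyond the protocol, since delivering 35 cc over 14 days most plainly means 2.5 ml/day. That is a fair reading, and the factor of 14 needs no flow assumption beyond it. But flow is nowhere stated, and the formula is there only so that the correction does not replace one wrong fixed amount with another.

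**Conclusion.** The concern holds. Section 5.1.4.6 is wrong as written: its floxuridine figure lacks the per-day unit that 1.6 states and that 1.7 and 5.1.3 imply. Followed literally, a 14-day infusion would deliver no more than 0.12 mg/kg instead of 1.68 mg/kg, at most 7.1% of the intended dose. The ratio does not depend on body weight. The milligram figures rest on the assumed 70 kg, and the shares below 7.1% on assumed flows under 2.5 ml/day.

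The direction is underdosing, not excess toxicity. The sample size, randomisation and error rates are untouched. It should be corrected because it sits in the instruction from which the investigational drug is prepared.

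**What to change.** In 5.1.4.6, state floxuridine as 0.12 mg/kg per day by continuous infusion over 14 days, matching 1.6, once the clinical team has confirmed that this is the dose. Give the amount per fill as a formula:

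0.12 mg/kg/day x dosing weight (kg) x 35 ml / actual pump flow (ml/day)

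Dosing weight follows the rule already in 5.1.4.6 for patients more than 25% above ideal weight. The formula equals 1.68 mg/kg only when 35 ml empties in exactly 14 days, so no fixed total should be written in.

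Send a notice to the trial hospital's pharmacy and HAI staff. The cost is a one-line protocol correction and that notice.

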5.1.4.8 Dose adjustments

Patients' complete blood counts and liver function tests are monitored every 2 weeks during HAIP chemotherapy. In the case of abnormal blood tests, dose reduction or postponement of HAIP chemotherapy is done according to the protocol (Table 2) that has been used at MSKCC for many years.

Table 2 complete blood counts and liver function tests:

	Reference Value (RV)*	% Floxuridine dose
Aspartate aminotransferase	2-3 * RV	80%
	3-4 * RV	50%
	>4 * RV	Hold
Alkaline phosphatase	1.2-1.5 * RV	50%
	>1.5 * RV	Hold
Total bilirubin	1.2-1.5 * RV	50%
	>1.5 * RV	Hold

**Reference value is defined as the patient's value on the first day of the most recent floxuridine dose.*

If treatment is held for any of the above situations, treatment will not be reinstated until values come down below 3* RV for aspartate aminotransferase or below 1.2*RV for alkaline phosphatase or total bilirubin, at which time treatment will resume at 25% of the last dose received.

If the patient develops a total bilirubin level above 51mmol/L (i.e. 3.0 mg/dL), the pump should be emptied and dexamethasone 25mg plus 35,000 U of heparin and enough normal saline to fill the pump reservoir should be placed in the pump for 14 days. Once there is no longer evidence of toxicity, the dexamethasone dose should be tapered in increments of 5mg every 14 days. Tapering will continue unless enzymes increase. Floxuridine should be permanently discontinued. Epigastric pain unresponsive to H2 blocker use should prompt a diagnostic workup including a technetium scan to rule out extrahepatic perfusion and an upper endoscopy to assess ulcer disease.

5.1.4.9 Duration of Therapy

Patients will receive HAI chemotherapy with floxuridine until progressive disease, until resection or until discontinuation due to toxicity or withdrawal of informed consent. After the end of adjuvant treatment the removal of the subcutaneous pump will be discussed with both the patient and the local expert panel. If the pump is removed, the catheter is tied off and will be left in place at the fascial level.

5.1.4.10 Expected toxicities

Systemic side effects with HAIP of floxuridine almost never occur; in particular, myelosuppression, nausea, and vomiting do not occur.(27) Diarrhoea is rare and should raise the suspicion of shunting of floxuridine to the bowel. Ulcer disease and biliary sclerosis are the most common toxicities. Ulcer disease results from inadvertent floxuridine perfusion of the stomach and duodenum that can be avoided by ligating all branches from the hepatic artery to the stomach and duodenum. Ulcer disease should be suspected when a patient develops severe epigastric pain after administration of the first dose. Diagnosis is confirmed with upper endoscopy and treated with embolization of the hepatic artery branch responsible for extrahepatic perfusion. If an ulcer or gastroduodenitis will be identified, therapy will be withheld for one month to allow healing. Pain treatment and proton-pump inhibitors will be started therapeutically. Severe abdominal pain or diarrhoea during hepatic arterial infusion will

require immediate emptying of the drugs from the pump and the instillation of heparin- treated saline until the result of the workup will be available.

The bile ducts are particularly sensitive to HAIP chemotherapy because they derive most of their blood supply from the hepatic artery. Close monitoring of liver enzymes and dose adjustment (as described in section 5.1.3) are necessary to avoid biliary sclerosis. Patients with severe biliary sclerosis may sometimes require percutaneous or endoscopic drainage and stent placement. A CT scan should be performed prior to biliary drainage to rule out intrahepatic recurrence causing biliary obstruction.

5.1.4.11 Expected complications related to the HAI pump

Surgical complications related to HAI pump placement may occur. A retrospective review of 544 HAI pump placements was performed at MSKCC.(19) Pump placement was typically combined with a partial liver resection. A simultaneous partial colectomy was performed in 136 patients (25%). No mortality attributed to the pump was reported. The most common complications were unrelated to the pump: wound infection of the laparotomy wound, atelectasis, prolonged ileus, and intra-abdominal abscess. Pump related morbidity (including dysfunction) occurred in 120 patients (22%). HAIP chemotherapy with floxuridine was impossible or discontinued in only 9% of patients. In 9 patients (2%) extrahepatic perfusion was found postoperatively, which could be resolved in 7 patients. In 9 patients (2%) postoperative technetium scan showed incomplete liver perfusion. Most common explanation was a non-ligated accessory or replaced hepatic artery, which was resolved with embolization or surgical ligation. Cross-over flow developed instantly or could be confirmed after four weeks. Hepatic arterial thrombosis can occur immediately after surgery (13 patients, 2%), of which a third could be salvaged with anti-coagulation. Thrombosis also occurred in 11 patients (2%) as a late complication resulting from HAIP chemotherapy. However, in the second half of the study only one patient developed a hepatic arterial thrombosis. The higher incidence in the first half was attributed to the intra-arterial administration of mitomycin C. Pump pocket infection was found in 24 patients (4%) and could be salvaged with parenteral antibiotics in half of these patients. In some patients with pump site infection, replacement and repositioning of the pump may be necessary. Simultaneous partial colectomy did not increase the rate of pump pocket infection. Arterial haemorrhage occurred in only 1 patient. The incidence of biliary sclerosis due to HAIP chemotherapy in a retrospective analysis of 293 patients was 5.5%. Risk factors most significantly associated with biliary sclerosis were dose, number of cycles, abnormal nuclear medicine scan, and postoperative infections. All patients were managed successfully with biliary stenting and/or dilatation.(28)

5.1.4.12 Expected toxicities related to the postoperative perfusion CT

Only a low dosage of radiation (15mSv) and a low dosage of contrast agent (5 - 10 ml) dosage are sufficient. These low numbers result in a negligible effect on renal function. The radiation dose is comparable to a diagnostic scan of the abdomen.

5.2 Drug Accountability - IMP

The responsible site personnel will confirm receipt of study drug and will use the study drug only within the framework of this clinical study and in accordance with this protocol. Receipt, distribution, return, and destruction (if any) of the study drug will be performed and documented according to the sponsor's standard operating procedures and according to agreement with the Department of Pharmacy.

5.3 Drug Labeling

The investigational product will have a label permanently affixed to the outside and will be labeled according with ICH GCP and national regulations, stating that the material is for clinical trial / investigational use only and should be kept out of reach of children.

The pharmacy will prepare and label the IMP in accordance with Norwegian requirements.

Labels will also include blank lines (in Norwegian) for:

- For Clinical trials administration
- Patient's initials
- Patient's enrolment code
- Protocol code
- Date dispensed
- Name of prescribing doctor
- Name of Principal Investigator

5.4 Subject Numbering, different arms of the study

Each subject is identified in the study by a unique subject number that is assigned when subject signs the Informed Consent Form. Once assigned the subject number cannot be reused for any other subject. STUDY procedures

5.5 Schedule of events

- Identification
 - Patients are identified from referrals or during MDT-meetings by surgeon or oncologist.
 - A trial specific MDT evaluation of liver metastases and resectability is performed.
 - Following this MDT-meeting, the patient is invited for out-patient visit within 10 days.
 - If no updated high-quality thoracic/abdominal CT and MR scan is available (No older than 4 weeks by date of out-patient visit), these are booked.
- At out patient clinic:
 - Eligibility for *Excalibur* 1 or 2 is assessed.
 - In house review of new images if applicable.
 - Eligible patients receive written and oral information about the trial and risks pertaining to HAI-catheter insertion/transplant/systemic chemotherapy
 - Measurement of CEA and standard blood chemistry
 - If patient consents:
 - Baseline QoL survey (C30) and EQ5D questionnaire is completed
 - Patient's latest CT or MRI scans are referred to next MDT meeting for designation of three target lesions for RECIST evaluation
 - Availability of mutation status is confirmed. If mutation status is not already performed, this is ordered from pathology lab.
 - Decision of eligibility for *Excalibur* 1 or 2 is decided by two trial investigators. If a patient is found to be eligibility for *Excalibur* 1 a member of transplant team will concur and provide specific information about transplants.
 - If a patient has begun or is planned for 2nd line chemotherapy, the randomization MUST take place before any evaluation of 2nd line treatment effect, i.e imaging (CT/MR). (PET for evaluation of extra hepatic disease is allowed). The choice of drugs for 2nd line chemotherapy must be decided on prior to randomization.
 - Inclusion is confirmed
 - Patient card
 - The following appointments are booked within two weeks:
 - A PET scan following 4 week chemo abstinence. If the patient has recently received systemic chemotherapy, a 4 week chemo abstinence must be ensured and randomization may need to be somewhat delayed.
 - Patients eligible for *Excalibur* 1 for individual assessment by transplant team
 - An operation theatre for insertion of HAI-pump catheter at four weeks from inclusion
- PI meeting two weeks following inclusion:
 - Documents, inclusion details, transplant assessment and PET results are reviewed

- If satisfactory, a web-based randomization is performed.
- All patients:
 - Monthly pregnancy testing should be performed in women of childbearing potential (WOCBP) as long as they receive chemotherapy according to study protocol. This can be done with a urine test at home combined with contact with the study team by phone
 - A calendar for oncologist visits and provision of systemic chemotherapy is created by coordinating nurse. Control scans are ordered for each 2nd month for the first year following randomization and as long as the patients receive chemotherapy, each 3rd month for the second year and each 6th month for the third year. MDT meetings are scheduled for one week following each new scanning to assess response and possible resectability
 - Out-patient control appointments are scheduled for outcome assessment including QoL-scoring (3, 6, 9, 15, 18, 21 and 24 months)
- Patients in HAI group (group 2 a and 2b)
 - A calendar of reservoir refills is created and harmonized with provision of systemic treatment.
 - A laparotomy is performed within 2 weeks from randomization with insertion of catheter and reservoir for HAI-pump.
- Patients in transplant group
 - Oncologists are instructed to avoid Avastin in systemic chemotherapy while the patient is listed.

Table 3: Overview of screening procedures, End of study/Withdrawal

Overview of screening procedures, End of study Withdrawal												
Item	ICF	Inc/Ex	Med Hist	Prior Trea	Phys Exam	Vit Sign	ECOG	CT/ MR	QoL	Blood Sample	Adverse Event	Survival Assessment
Screening	x	x	x	x	x	x	x	x	x	x	x	
EOS/Withdrawal											x	x

Table 4: Calendar of cycles and events for patients in HAI group

Calendar of cycles and events for patients in HAI group								
Day cycle 1 + 2	1	2	15	16	29	30	44	
Day cycle 3 + 4	61	62	75	76	89	90	104	
Pump refill FUDR at OUS	x				x			
Pump refill HepNaCl at OUS			x					x
Systemic chemo local hospital		x		x		x		

Table 5: Calendar of cycles and events for patients in control group and on waiting list for LTx-group

Calendar of cycles and events for patients in control group and on waiting list for LTx- group							
Day cycle 1 + 2	1		15		29		44
Day cycle 3 + 4	61		75		89		104
Systemic chemo local hospital	x		x		x		x

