5.6.3 Progressive disease or toxicity

In the case of progressive disease (PD) in the systemic chemotherapy arm, this treatment will be halted and shifted to 3rd chemotherapy as appropriate or to best supportive care (BSC). In the case of PD in the HAI-group, systemic chemotherapy will be changed to 3rd line as appropriate and the use of pump is discontinued. In the case of PD in the transplant group, listing is upheld but chemotherapy is changed to 3rd line as appropriate until available organ is available. In the case of toxicity a change in systemic chemotherapy to 3rd line is attempted and if unaltered toxicity, halted.

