5.6.5 After End of Treatment (Follow-up)

Patients having a liver resection or liver transplantation will have follow-up according to Table 6-7. These patients will have follow-up until 10 years after surgery or until they start palliative treatment.

Table 6. Follow-up of resected Excalibur study patients

Follow up Ltx patients	Visits 1 st year (every month)	Visits 2 nd year (every 3 month)	Visits 3 rd -10 th years (every 6 month)
Hb CRP, Hv, Trc, Na, K, Crea	X	X	X
Bilirubin, ASAT, ALAT, ALP, Alb	X	X	X
INR, Cholesterol, glucose, HbA1c	X	X	X
CEA, CA 19-9,	Every 3 months	X	X
TIMP-1, TPA (stop at relapse)	Every 3 months	X	X
5 ml EDTA plasma for later analyses (until relapse)	Every 3 months	X	X
5 ml serum for later analyses (until relapse)	Every 3 months	X	X
Weight	X	X	X

BP	X	X	X
CT thorax/abdomen/pelvis (only in Ltx patients without relapse)	Every 2 months	Every 3 months	Every 6 months
US Liver w/Doppler (only Ltx patients)	Every 3 months		
Coloscopy (only in Ltx patients without relapse)	At 12 months	At 36 months	At 60 months
PET scan (only in patients without lesions on CT)	At 12 months	At 24 months	
EORTC QLQ-C30 and EQ5D	3, 6, 12, months	2 times/year	2 times 3.year

Table 7 Follow-up of Control group, HAI-group and patients not receiving LTx

arm		Outcome	Palliative treatment	Follow Up
3 and 2	Chemo therapy	Surgery	No	10 Years
	FUDR/HAI	PD/Toxicity	yes	Will do "End of treatment visit". OS will be collected.
1	Liver Tx	Transplant	No	10 Years.
		Extra-hepatic disease	yes	Will do "End of treatment visit". OS will be collected.
		Metastasis to lymphnodes	yes	Will do "End of treatment visit". OS will be collected.

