8 STATISTICAL METHODS AND DATA ANALYSIS

8.1 Determination of Sample Size

We estimate an overall survival at two years in the standard care group (group 3) to be 30 %. We aim to decide whether the use of HAI (group 2) can increase this to 75 % and if liver-TX (group 3) can increase this to 90 %. For a two-sided parallel-group test of proportions to answer both questions with a power of 0.80 and an alpha of 0.05, this will require 16 completed patients per group 3 and 2 to show superiority for HAI over standard care (systemic chemotherapy). An additional 7 patients is needed in the transplant group (1) to show superiority over standard care group (3), bringing the total to 39 patients. This is based on a three-year accrual time, and a total of five-year follow-up from the first patient, ensuring at least two years follow-up for all patients. The trial is not powered to show a difference between group 2 and 1. Adding 15 % to allow for drop-outs, we aim to randomise a total of $18 + 18 + 9 = 45$ patients in a 2:2:1 ratio.

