8.5.2 Secondary analyses

- Per-protocol comparison of overall survival at 2 years
- ITT liver-progression-free survival,
- Rates of liver resection in HAI group compared with control group and with transplantation rate for TX group. Standard approximation to binary outcomes with Fisher exact test or chi-square.
- Quality-of-life as measured by EORTC-30

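### The rules for collecting quality of life in Section 5.5, Table 6 and Table 7 are not reconciled: month 12 is absent, post-surgery visits run on another clock, and collection after progression is unclear and differs by arm

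*Protocol*

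**What the plan says.** **All patients.** Protocol Section 5.5 sets a baseline at consent: "Baseline QoL survey (C30) and EQ5D questionnaire is completed". Its block for all patients then states: "Out-patient control appointments are scheduled for outcome assessment including QoL-scoring (3, 6, 9, 15, 18, 21 and 24 months". The list has no month 12 and no stopping rule. It names no time origin, but the scan schedule in the same block counts from randomisation.

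**After surgery.** Section 5.6.5 places resected and transplanted patients on Tables 6 and 7 and adds: "These patients will have follow-up until 10 years after surgery or until they start palliative treatment". Table 6 sets QLQ-C30 and EQ5D at 3, 6 and 12 months, twice in year two and twice in year three.

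**After progression (PD).** For control and HAI patients with PD or toxicity, Table 7 gives an end-of-treatment visit and then "OS will be collected". In the transplant arm the same entry is tied to extra-hepatic disease and to lymph-node metastasis. The end-of-study/withdrawal row of Table 3 marks adverse events and survival, not QoL. Section 5.6.3 says "In the case of PD in the HAI-group, systemic chemotherapy will be changed to 3rd line as appropriate and the use of pump is discontinued", but "In the case of PD in the transplant group, listing is upheld".

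**Analysis.** The synopsis and Table 1 list QoL as a secondary endpoint. Section 8.5.2 names it as "Quality-of-life as measured by EORTC-30", without a time point.

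**The concern.** Sites will book questionnaires from these tables, and different staff can follow different ones in good faith. Three questions are open: whether a 12-month assessment exists, whether an operated patient is assessed from randomisation, from surgery or both, and whether a patient who has progressed is still asked.

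The third matters most. If questionnaires end when control and HAI patients progress, while a transplant-arm patient with progression confined to the liver continues, missing data depend on both arm and outcome. Patients still answering in the control and HAI arms would be those doing well. In an open-label comparison of chemotherapy with major surgery, that selection can bias the QoL contrast. EQ5D is collected at the same visits, and the synopsis plans a health economy assessment, so the same gaps would reach that data too. A later analysis plan can choose a missing-data method, but it cannot recover questionnaires that were never handed out.

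**Working it through.** The plan attaches no figure to this point, so there is none to reproduce. The check sets the rules side by side, compares the calendars, and then asks what can be said about size.

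**1. Rules side by side**

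| Source | Applies to | QoL times | Clock | End of collection |
|---|---|---|---|---|
| Section 5.5 | all patients | 3, 6, 9, 15, 18, 21, 24 months | randomisation (inferred from the scan schedule) | none stated |
| Table 6 | resected or transplanted | 3, 6, 12 months; twice in year 2; twice in year 3 | surgery | palliative treatment, otherwise year 3 for QoL |
| Table 7, control and HAI | PD or toxicity | not mentioned | – | end-of-treatment visit, then survival |
| Table 7, transplant arm | extra-hepatic disease or nodal metastasis | not mentioned | – | end-of-treatment visit, then survival |

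Table 7 has no row for transplant-arm progression confined to the liver. This agrees with Section 5.6.3, where listing continues. The same event therefore leads to different follow-up by arm.

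**2. Calendars**

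Let A = {3, 6, 9, 15, 18, 21, 24}. For surgery at month s after randomisation, Table 6 gives B(s) = s + {3, 6, 12, 18, 24}, assuming that twice in year two means 18 and 24 months after surgery. Take s = 0, 1, …, 12, exact months, and visits up to month 24.

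| Surgery month s | Months in both A and B(s) |
|---|---|
| 0 | 3, 6, 18, 24 |
| 3 | 6, 9, 15, 21 |
| 6 | 9, 18, 24 |
| 9 | 15, 21 |
| 12 | 15, 18, 24 |
| 1, 2, 4, 5, 7, 8, 10, 11 | none |

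Every entry in both lists is a multiple of three, so the calendars can meet only when s is too. They share nothing for 8 of 13 values. Month 12 after randomisation is never in A. It is in B(s) only for s = 12 − 12 = 0, 12 − 6 = 6 or 12 − 3 = 9.

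This comparison matters only if Table 6 **replaces** the Section 5.5 list. If Table 6 **supplements** it, all arms share the seven months in A and only month 12 is missing. A visit window of one month either side would restore some matches for every s, but A would still have no visit between months 11 and 13.

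**3. What can be sized**

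Section 8.1 gives two-year survival of 30% (control), 75% (HAI) and 90% (transplant), with 18, 18 and 9 patients. Assuming exponential survival, the number alive at month 12 is n × S(24)^(12/24):

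- control: 18 × 0.30^0.5 = 18 × 0.548 = 9.9
- HAI: 18 × 0.75^0.5 = 18 × 0.866 = 15.6
- transplant: 9 × 0.90^0.5 = 9 × 0.949 = 8.5

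These are ceilings on the number who could answer at one year under any schedule. How many of the roughly 10 living controls would have progressed by then, and so be exposed to the Table 7 rule, cannot be derived: the protocol states no progression-free survival.

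**The case against.** The best defence is that the Section 5.5 list is headed for all patients and nothing withdraws anyone from it. Read that way, every arm has a baseline and seven common assessments, Table 6 is extra, and the one gap is month 12, probably a typing omission. No planned analysis names month 12. Analysis time points and missing-data handling can properly be left to the statistical analysis plan, and comparison among survivors is unavoidable for QoL in lethal disease.

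Much of this stands, and it rules out several stronger readings:

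- **The arms share only months 3 and 6.** A reader might infer this from the two lists. It would require Table 6 to replace the all-patient list, which the protocol does not say.
- **QoL stops at progression.** Tables 3 and 7 suggest it for control and HAI patients, but no sentence says so, and Section 5.5 runs to month 24 without a stop.
- **Operated patients continue for years while the others drop out.** Operated patients also leave follow-up when palliative treatment starts, and Table 6 sets no QoL beyond year three. Control and HAI patients who are resected enter the same surgical follow-up. The split is therefore partly by outcome, not simply by arm.
- **A percentage of controls without one-year QoL.** Any such figure needs an assumed progression time that the protocol does not give. It would also count deaths as missing questionnaires: on the Section 8.1 survival rate, about 18 − 9.9 = 8.1 of 18 controls would have died by month 12.

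The defence does not answer the conflict itself. That Table 6 is additional, and that Section 5.5 overrides Table 7, are both assumptions, and the collection calendar belongs in the protocol.

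**Conclusion.** The concern holds as a conflict between collection rules for a declared secondary endpoint. Two parts are certain from the text: month 12 is missing from the all-patient list, and the post-surgery schedule is not reconciled with that list. A third part is conditional. If Table 7 is taken to govern QoL, collection would end at progression or toxicity for control and HAI patients but not at progression alone for transplant-arm patients, and the QoL comparison would be biased by arm- and outcome-dependent missing data.

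The size lies between two readings. If Section 5.5 governs throughout, only month 12 is lost. If Table 6 replaces the list after surgery, the calendars share no exact visit up to month 24 for 8 of 13 surgery months, on the stated assumption about year two. The additional loss under Table 7 cannot be quantified from the protocol.

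The primary overall survival analysis is unaffected. The point should be corrected because the lost data cannot be recovered later, but it does not threaten the trial's main conclusion.

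**What to change.** - In Section 5.5, state one QLQ-C30/EQ5D calendar for all arms, timed from randomisation: baseline, then 3, 6, 9, 12, 15, 18, 21 and 24 months.
- State that it continues after progression, end of treatment and surgery. Post or telephone is acceptable when the patient no longer attends.
- State in Table 6 that its questionnaires are additional to this calendar.
- Amend Table 7 so that QoL as well as survival is collected to 24 months in every arm, and make the end-of-study row of Table 3 agree.

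These changes concern questionnaires only and leave treatment and listing rules as they are. The cost is one extra questionnaire time point per patient and some coordinator time for forms after progression.
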